Very little formal investigation has been performed to study the influence of age on hip arthroscopy outcomes; as such, there is currently no consensus on age as a predictor of outcome. Khanduja and Villar¹² recommend arthroscopy to be reserved for patients aged less than 50 years old. Philippon et al.³² reported outcomes after FAI in patients aged 50 years or older at a minimum 1-year follow-up and found that patients primarily achieved surgical success, though with a 20% conversion to total hip replacement (with a higher incidence in patients with > 2 mm of joint space). Larson et al.²⁴ also showed a failure rate that was dependent on age; however, a formal comparison was not made. Byrd and Jones³⁹ showed worse outcomes in older men. Although there have been studies looking at age secondarily in patients with labral tears, there is no prospective evidence to endorse or refute a recommendation of hip arthroscopy for patients of any age being treated for a tear of the acetabular labrum.

Preliminary Data

Our group recently performed a large retrospective case-control series looking at the influence of pre-operative arthritis and age as predictors of long-term outcomes following arthroscopic labral repair.⁴⁰ Over the course of the study period, which spanned 8 years and 200 patients, our management evolved to reflect the current practice of abstaining from arthroscopy in patients with less than 2 mm of joint space on plain standing radiographs. In spite of this, we continue to routinely encounter cartilage defects intra-operatively. Such findings can be explained by evidence stating conventional radiographic measures are poor predictors of actual arthritis in the hip.⁴⁸ Although it is possible that focal cartilage defects seen at arthroscopy are incidental findings.⁴²

Most studies attempt to eliminate radiographically evident severe arthritis by excluding patients who demonstrate less than 2 mm of joint space on standing antero-posterior hip radiographs at the time of surgery. However, based on our results, we suggest that the presence of Outerbridge grade 4 arthritic changes noted at the time of arthroscopy can be used adjunctively to identify patients who will fare poorly after hip arthroscopy for labral pathology. Interestingly, despite the apparent influence of arthroscopically identified arthritis portending worse outcomes (Odds ratio=2.5), our preliminary results suggest age is a stronger predictor (Odds ratio = 7) of diminished surgical outcomes.

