Most recently, the authors involved in this study performed a retrospective investigation (unpublished data) to capture patients with clinically and radiographically confirmed acetabular labral pathology electing to undergo conservative management defined as the refusal of surgical intervention. Based on a retrospective review of 894 patients presenting to clinic over a 10-year period, we identified 22 patients with labral pathology that were treated non-operatively. Retrospective case control analysis was performed using outcome questionnaires administered to both surgical and non-surgical cohorts. We found that patients with labral tears managed non-operatively appear to score highly on hip function outcome scores, preliminarily indicating there may be some benefit in using conservative management alone in the treatment of labral pathology. Controlled comparative analyses between surgically and non-surgically managed patients suggested that non-operatively managed patients exhibit a non-significant tendency toward worse outcome.

Given the lack of current guidance for judicious use of hip arthroscopy for labral pathology in patients of increasing age with arthritic change, we propose that there is a need for high quality prospective comparative studies assessing hip arthroscopy against physical therapy as a non-operative form of management for tears of the acetabular labrum. Furthermore, preliminary evidence by our group and the published data of others described above highlights the necessity for continued investigation into

this topic with particular emphasis on the role of preexisting arthritic change in this select group of patients. Without prospective investigation into the role of arthritic burden and age, we cannot begin to fully assess their influence on outcomes following labral repair.

Implications:

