Our Primary Outcome is change in the modified Harris Hip Score at 12 months and 24 months. Secondary outcomes include changes in other validated outcomes measures patient satisfaction, and degree of improvement on physical exam. The influence of OA severity (Outerbridge scoring) and location of OA will also be analyzed to determine if they have an effect on the aforementioned outcome measures. Satisfaction will be assessed by an exit questionnaire (See section IV). In addition to gauging satisfaction, this questionnaire will ask subjects how they felt about their participation in the study. (See section IV)

Inclusion and Exclusion Criteria:

Inclusion criteria	Rationale
Age 40 or greater	Higher likelihood of undetectable OA on imaging
Orthopedic surgeon determines symptoms are consistent with a labral tear.	Required for treatment
Availability of hip radiographs and MRI	Needed to assess eligibility and comparison for specific aim 3
Willingness to undergo randomization and ability to understand and sign informed consent document	Ability to understand study and consent willingly

Exclusion criteria	Rationale
Unexpected pathology at the time of arthroscopy	Source of pain less likely to due dysfunction of the labrum and more likely due to aberrant extra-articular biology
Same site surgery	Complex anatomy
Contraindication to surgery or physical therapy	Cannot tolerate either treatment grouping
Alternate form of PT for greater than 6 weeks	Will negatively augment results. May affect recruitment.

Selection and enrollment:

We will enroll 122 consecutive subjects meeting the aforementioned criteria. Subjects will be randomized into conservative or surgical treatment arms. All potential subjects on the clinic schedule of the investigator will be pre-screened for eligibility based on age, clinical assessment, and previous medical history.

All eligible subjects will be approached at an outpatient clinic visit. Those who initially meet inclusion criteria will be introduced to the study and given a research consent form that they have the opportunity to take home and to review.

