The research coordinator will randomize the subjects into the study at this visit. Randomization will be assigned utilizing an electronic randomization program. Those receiving conservative management will be scheduled for physical therapy. Those receiving surgical management will be scheduled for surgery and the post-operative physical therapy protocol within 2 weeks of their operative date.

Efforts will be made to attain a mix of study participants, regarding gender and racial/ethnic representation reflective of the population of the greater metropolitan Boston area: 66% White, 14% African American and 10% Hispanic or Latino. More specifically, we anticipate that at least half of our subjects will be female and that we will have representation from Asian American, African American and Hispanic minority groups in our final cohorts.

Informed consent:

The informed consent document will be approved by the IRB at Partners HealthCare, which covers The Brigham and Women's Hospital, Faulkner Hospital, and the Brigham and Women's/Mass General Health Care Center at Foxborough. The informed consent process will be conducted by the PI.

Overview of sample size:

This randomized control trial includes 122 subjects age 40 or older with evidence consistent with tears of the acetabular labrum in the affected hip

Meeting recruitment targets:

As previously mentioned, the design of our study is similar to that of the MeTeOR trial ⁴³ in which [name] and [name] were lead investigators. [name] was the highest referral base for the

MeTeOR subjects at the BWH site and [name] designed, delivered and managed the physical therapy protocol for both arms of the MeTeOR trial across 7 national trial centers. Based on a survey before that trial commenced, it was estimated that 20-25% of eligible subjects would agree to participate in the randomized controlled trial. Participation in the actual trial was 26%. We anticipate a similar recruitment percentage as our design is similar as are our inclusion criteria.

Study retention procedures:

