The mean outcome scores of the mHHS in each treatment group at 12 months will be compared to baseline scores to assess for significant differences using paired sample t-test in SPSS 16 (SPSS, Chicago, IL). The mean outcomes scores of the mHHS between groups at 12 months will be compared using independent t-tests to assess for significant difference. We will use a Levene test to judge variance and proceed accordingly. If a statistically significant difference is detected during these analyses, we will calculate the effect size (ES) to determine how meaningful these results are outside of being statistically significant. The ES will be calculated by: [(mean mHHS score of surgical arm / mean mHHS of the conservative group) / standard deviation of the conservative group]. According to Cohen ⁵⁸, an ES <0.1 is trivial, ES of 0.1-0.3 is minimal, ES of 0.3-0.5, is moderate, and ES >0.5 is large. We will repeat the same analysis at 12 months.

Hypothesis 2.1, 2.2, and 2.3:

Diagnosis and treatment of the prearthritic and early arthritic hip has been an area of intense interest. However, our most conventional method of assessment (plain radiography) does not provide us with enough diagnostic sensitivity.⁴¹ Direct visualization on the articular surfaces in the hip is both sensitive and specific. Furthermore, emphasis is being placed on the location of arthritis as a prognostic indicator of good outcomes following hip arthroscopy. The value of arthroscopic techniques for primary

symptoms and/or prevention of OA secondary to labral tears remains unclear even though preliminary reports indicate there may be some benefit to repairing a torn labrum, even in cases of severe OA. Evaluation of arthritic change at the time of arthroscopy is important, particularly in subjects where there remains uncertainty about the efficacy of labral repair for those with articular or rim cartilage degeneration that the effects of those changes on long-term OA progression.⁵⁹

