Using the data from our retrospective review of outcomes following labral repair, a 10 point or greater difference on the mHHS as significant, and a single-tail independent t-test to evaluate the difference between means with 80% power and a 5% significance level, 35 subjects are needed to demonstrate a statistically significant difference between the average mHHS of the conservative group and surgical group. Testing of hypothesis 1.5 will be an intragroup analysis looking for a significant difference in outcome measures from the time of completion of PT (non-crossover) when compared to the same data to be collected at 12 months and 24 months. The purpose is to determine the short-term durability of the response to PT, if one is found.

70 study completers should provide us with the necessary data needed to substantiate or reject our hypothesis. There has been no prospective trial to date testing these hypotheses in the hip, but we expected a 7.3-10.3% dropout rate based on the results of a similar study in the knee. However, as of July 2018, we had 47 patients that had passed the 2-year follow-up mark, of which 5 patients were no longer in the study (combination of lost to follow-up and proceeding to total hip arthroplasty), and another 11 had yet to complete their 2-year surveys even with multiple attempts to contact them and encourage them to do so. With a yield of 31 patients out of 47, or 65.95%, we increased our sample size to 122.

Therefore, we estimate needing 122 subjects to achieve 70 study completers, in the appropriate proportion of 35 subjects per treatment arm. We enroll until reaching at least 35 subjects in each group.

The results of the MeTeOR trial in the knee show that we can expect a higher drop-out rate in the surgical group. As such, this cohort may be our limiting factor.^{40, 43, 61, 62}

Specific Aim 2. Hypotheses 2.1-2.3: *To evaluate the significance of arthritic burden on short term outcomes following arthroscopic labral repair.*

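### The between-arm test for Hypothesis 1.3 leaves out age, which the plan's own preliminary data report as prognostic; a prespecified age covariate costs almost nothing, but its gain is uncertain and may be small

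*Combined protocol and SAP*

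**What the plan says.** Section V (Biostatistical Analysis, Hypothesis 1.1-1.4) sets the between-arm test: "The mean outcomes scores of the mHHS between groups at 12 months will be compared using independent t-tests to assess for significant difference". A Levene test decides how variance is handled. No covariate is mentioned. The regressions described elsewhere in section V concern osteoarthritis severity and joint space narrowing under Aim 2, not the arm comparison.

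Section I (Preliminary Data) reports from the group's retrospective labral repair series that "our preliminary results suggest age is a stronger predictor (Odds ratio = 7) of diminished surgical outcomes". The comparison there is with arthritis seen at arthroscopy, which has an odds ratio of 2.5. The same section adds: "Without prospective investigation into the role of arthritic burden and age, we cannot begin to fully assess their influence on outcomes".

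Section III makes age 40 or older an inclusion criterion and says that potential subjects "will be pre-screened for eligibility based on age, clinical assessment, and previous medical history". Age is therefore on record for everyone before allocation. On allocation itself, the section says only: "Randomization will be assigned utilizing an electronic randomization program".

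The Power Analysis in section V takes "a 10 point or greater difference on the mHHS as significant" and uses "a single-tail independent t-test to evaluate the difference between means with 80% power and a 5% significance level", arriving at 35 completers per arm.

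**The concern.** A baseline variable that predicts the outcome can be put into a randomised comparison to reduce residual variance and to correct for whatever imbalance chance produces. The plan identifies such a variable, holds it for every subject, and does not use it in its main between-arm test. With 35 completers per arm, any mHHS variance explained by age stays in the error term, and a difference in mean age between the arms would move the estimated treatment effect with no planned correction. An adjustment added after the data are seen would be open to challenge.

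This is separate from the absence of baseline mHHS from the same test, because age may explain variation in response that the baseline score does not. It is also separate from age as a confounder in Aim 2, which concerns operated hips only.

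**Working it through.** **Inputs from the plan.** 35 completers per arm, a 10-point difference, one-sided 5%, 80% power (section V, Power Analysis); odds ratio 7 for age (section I, Preliminary Data).

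**Not in the documents, so assumed and varied.** The SD of mHHS, the correlation r between age and 12-month mHHS, the age cut-point behind the odds ratio, the share p of subjects in the older group, and any age effect under physical therapy.

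**1. The plan's figure.** Because no SD is given, 35 per arm cannot be reproduced directly. Solving backwards, a one-sided t-test with 68 degrees of freedom and non-centrality d × √(35/2) has 80% power at d = 0.600. The implied SD is 10 / 0.600 = 16.7.

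**2. Power with age in the model.** The residual SD becomes SD × √(1 − r²), so the standardised effect is 0.600 / √(1 − r²), with 67 degrees of freedom.

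| Assumed r | Variance removed (r²) | Power |
|---|---|---|
| 0 | 0% | 80.0% |
| 0.2 | 4% | 81.4% |
| 0.3 | 9% | 83.2% |

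**3. What odds ratio 7 would imply at full strength.** The logistic conversion to a standardised difference is ln 7 × √3/π = 1.946 × 0.5513 = 1.073. Then r = 1.073 / √(1.073² + 1/(p(1 − p))).

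**4. The same odds ratio acting only after surgery.** This is the only setting in which the documents report an age effect. With equal arms and equal SDs, the common slope is half the surgical slope. It removes 3r²/4 of the variance in the surgical arm and adds r²/4 in the physical therapy arm. The average removed is (3r²/4 − r²/4)/2 = r²/4.

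| Older share p | r | Power, effect in both arms | Power, surgical arm only |
|---|---|---|---|
| 50% | 0.47 | 88.0% | 82.0% |
| 30% | 0.44 | 87.0% | 81.7% |
| 20% | 0.39 | 85.6% | 81.4% |
| 10% | 0.31 | 83.3% | 80.8% |

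If r were only 0.2-0.3 and the effect were also confined to the surgical arm, power would be 80.3-80.8%.

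**5. Chance imbalance.** If allocation does not balance age, the difference in mean age between arms, in age-SD units, has a standard error of √(2/35) = 0.239. A difference above 0.25 SD in either direction then has probability of about 30%, and one above 0.5 SD about 4%. With the same age slope in both arms, a 0.5 SD imbalance shifts the unadjusted difference by 0.5 × r × 16.7. That is 1.7 points at r = 0.2 and 2.5 points at r = 0.3, against a 10-point target.

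**6. What cannot be computed.** All these figures compare age adjustment with no adjustment at all. The gain from age on top of baseline mHHS depends on correlations that the documents do not give, and may be smaller.

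**The case against.** The strongest reply is that nothing here is wrong: the plan powers on an independent t-test and analyses with one, and under randomisation that test is valid. This stands. The point concerns efficiency and a missing prespecification, not bias.

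Several stronger readings are tempting, and the documents do not support them.

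- A reader might infer that power would rise to 86-88%. That needs the full odds ratio to apply in both arms, with 20-50% of subjects in the older group. The odds ratio describes surgical outcomes in a retrospective series, has no stated cut-point, and may reflect an age range that the age-40 criterion has already narrowed. It also relates to a dichotomised outcome, so its conversion is only a rough guide to what continuous age would explain in mHHS.
- A reader might infer that the plan ranks age above all other predictors. It ranks age above arthroscopic arthritis only and calls the results preliminary. The Age subsection of section I also says that opinion on age as a predictor is unsettled.
- A reader might infer that randomisation is unstratified. The settings of the program are not described, so nothing can be concluded either way. If it does balance age, age belongs in the model all the same.

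It can also be said that 80% is a floor. The plan enrols until each arm has at least 35, and 122 × 31/47 is about 80 completers. At 40 per arm, unadjusted power would be 84.5%. That yield is a two-year figure, however, and the plan expects heavier drop-out in the surgical arm, so an even split is not assured.

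Finally, an age effect confined to surgery would be an age-by-treatment interaction, which an additive covariate does not describe. True; step 4 of the working shows that the gain is then only 1 to 2 points.

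**Conclusion.** The point holds as a low-cost improvement. The direction is secure: age is available before allocation, the plan's own data suggest that it is prognostic, and the Hypothesis 1.3 test does not use it. The size is not secure. On the plan's inputs, a reasonable expectation is power of about 81-83% instead of 80%, assuming r of 0.2-0.3 in both arms, or about 81-82% if the odds ratio of 7 acts only after surgery with 20-50% of subjects in the older group. The 86-88% range is an upper bound under assumptions that the documents do not establish. The benefit beyond baseline mHHS is unknown. The second benefit, a prespecified correction for chance age imbalance, is worth having even where the power gain is slight.

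**What to change.** In section V, replace the independent t-test for Hypothesis 1.3 with a prespecified linear model of mHHS on randomised arm, with age as a continuous covariate. If adjustment for baseline mHHS is adopted, put both covariates in the same model. Use this model at 12 months and, for Hypothesis 1.4, at 24 months. Report the unadjusted difference as a supportive result.

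The cost is about one line of SAP wording. Age is already recorded for every subject, so no new data are needed and no subject is lost for a missing covariate. One degree of freedom is used: if age explained nothing, power at 35 per arm would still be 80.0%.

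### Minor: an underspecified Levene pretest picks the between-arm t-test, and the error rate drifts slightly from 5% if arm sizes and variances both differ

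*Combined protocol and SAP*

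**What the plan says.** In Section V, under Hypothesis 1.1-1.4, the mean mHHS scores of the two arms at 12 months "will be compared using independent t-tests to assess for significant difference". The next sentence adds: "We will use a Levene test to judge variance and proceed accordingly". The section names neither the pooled nor the unequal-variance form. It does not give the Levene significance level, say what follows from each result, or say whether the t-test is one- or two-sided.

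The Power Analysis for Specific Aim 1 is based on "a single-tail independent t-test to evaluate the difference between means with 80% power and a 5% significance level". It takes "a 10 point or greater difference on the mHHS as significant" and describes its source as "Using the data from our retrospective review of outcomes following labral repair", but prints no SD for either arm. The target is 70 completers "in the appropriate proportion of 35 subjects per treatment arm".

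Two further statements there bear on balance. Recruitment has a floor, not a fixed split: "We enroll until reaching at least 35 subjects in each group". And, citing a knee trial, the plan says "we can expect a higher drop-out rate in the surgical group", without giving an amount.

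**The concern.** If the variance pretest decides which t-test is used, the final test depends on a second random result from the same data. The pooled test is the one used whenever Levene fails to reject, and at this sample size that will often happen even though the SDs differ moderately. With equal arms this does no harm. With unequal arms the pooled standard error is too small if the smaller arm is the more variable one, and too large in the reverse case. The plan itself expects the surgical arm to lose more patients.

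At stake is a small error in the p-value, and in any interval reported with it, for the primary comparison. Its direction cannot be known in advance, because no arm-specific SD is given. Separately, a reader cannot tell from the text exactly which test will be run.

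**Working it through.** **The plan's own figure.** The SD is not printed, so 35 per arm cannot be reproduced directly, only inverted. With n = 2(z₀.₉₅ + z₀.₈₀)² SD²/Δ², Δ = 10 and n = 35:

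SD = 10 × √[35 / (2 × (1.645 + 0.842)²)] = 10 × √(35/12.37) = 16.8

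The t-based value is 16.7. The target is therefore consistent with a one-sided 5% test, 80% power and a common SD near 16.7. That SD is used below only for power.

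**How unequal the arms might be (assumed).** The plan reports a yield of 31/47 = 65.96%, and 122 × 0.6596 ≈ 80 completers. A surgical arm that just reaches 35 would leave 45 in the other arm. A 35/52 split needs 87 completers, and 35/61 needs 96. Both exceed that yield and serve as outer cases. A 25/45 split keeps the total of 70 but breaks the floor of 35; it is a stress case. SD ratios are also assumed.

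**Why both must differ.** The true variance of the mean difference is s₁²/n₁ + s₂²/n₂. The pooled test uses sₚ²(1/n₁ + 1/n₂), where sₚ² = [(n₁−1)s₁² + (n₂−1)s₂²]/(n₁+n₂−2). Take n = 35 and 45.

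- SD 1.5 in the smaller arm, 1 in the larger: true 2.25/35 + 1/45 = 0.0865. Pooled (34×2.25 + 44)/78 × (1/35 + 1/45) = 1.545 × 0.0508 = 0.0785. The pooled standard error is too small by 1 − √(0.0785/0.0865) ≈ 5%.
- SDs reversed: true 1/35 + 2.25/45 = 0.0786. Pooled (34 + 44×2.25)/78 × 0.0508 = 0.0866. It is too large by about 5%.
- With n₁ = n₂, or with s₁ = s₂, the two expressions agree.

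**Simulation of the two-stage rule.** Normal data, 200,000 trials per setting, mean-centred Levene at 5% (assumed), then pooled or Welch. The simulation error is √(0.05×0.95/200,000) ≈ 0.05 percentage points.

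| Completers | SD ratio, larger SD in | Levene detects | Two-stage, two-sided | Two-stage, one-sided | Welch, two-sided |
|---|---|---|---|---|---|
| 35/35 | 1.3, either arm | 29% | 4.97-5.00% | 4.96-5.08% | 4.95-4.99% |
| 35/35 | 1.5, either arm | 58% | 4.96-5.06% | 5.03-5.04% | 4.95-5.04% |
| 35/45 | 1.3, smaller arm | 33% | 5.38% | 5.27% | 4.96% |
| 35/45 | 1.3, larger arm | 31% | 4.64% | 4.80% | 4.98% |
| 35/45 | 1.5, smaller arm | 64% | 5.26% | 5.13% | 4.94% |
| 35/45 | 1.5, larger arm | 62% | 4.68% | 4.81% | 4.95% |
| 25/45 | 1.5, smaller arm | 56% | 6.06% | 5.76% | 5.04% |
| 25/45 | 1.5, larger arm | 52% | 4.22% | 4.42% | 4.93% |

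At 35/52 with SD ratios of 1.25-1.5, the two-sided error was 5.4-5.6% with the smaller arm more variable and 4.5-4.8% in the reverse case. At 35/61 it spanned 4.4-5.8% over all ratios tried. With equal SDs it was 5.0% at every imbalance. At 35/35, Levene detection rises from 22% at ratio 1.25 to 84% at 1.75 and 95% at 2. At ratio 2 the two-stage error is back near 5%.

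**Cost of Welch throughout** (SD 16.7, difference 10, equal variances, one-sided power, pooled then Welch): 79.9% and 79.8% at 35/35; 83.8% and 83.7% at 35/45; 76.7% and 76.4% at 25/45. The largest two-sided loss is 65.8% to 65.3%, at 25/45.

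**Skewed scores.** Section IV describes the mHHS as bounded at 0 and 100.1, so the check was repeated on skewed bounded data. Two-sided error was 5.0-5.5% for Welch and 4.6-6.2% for the two-stage rule. One-sided it was 4.2-6.9% and 4.2-7.8%. With equal SDs at 25/45, one-sided Welch gave 5.8% against 5.2% for the two-stage rule, and its power was 74.4% against 76.4% for the pooled test.

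**The case against.** The strongest reply is that nothing is wrong at the design as planned: with 35 completers in each arm the two-stage rule keeps 5% whatever the variances. That is correct. So is the reply that unequal sizes alone do no harm. A reader might infer that the surgical dropout the plan expects is enough to move the error rate. It is not, because the variances must differ too, and the documents give no SD for either arm.

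A reader might also infer that Levene is of little use here. That is too broad. It finds an SD ratio of 1.5 more often than not and a doubling nearly always, so it misses mainly modest differences. It also removes most of the error of an ungated pooled test, which at 25/45 and ratio 1.5 runs at 8.0% or 3.0% two-sided.

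Nor is Welch's test free or exact in every setting. On skewed scores it can lose about 2 power points, and a one-sided Welch test departs from 5% too. With equal SDs and skew it can do slightly worse than the planned rule.

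Finally, the rule is declared in advance, and a shift of about half a point would be unlikely to change the trial's conclusion. What survives is narrower. Unequal completers are foreseeable from the plan's own statements, the rule is not fully written down, and a simpler choice avoids the drift on normal data at almost no cost.

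**Conclusion.** The point stands as a minor refinement. The two-stage rule shifts the two-sided error from 5% to roughly 4.5-5.6% under assumed splits of 35 versus 45-52 completers and assumed SD ratios of 1.25-1.5, and slightly less one-sided. The error is above 5% if the smaller arm is the more variable and below it in the reverse case. There is no distortion at 35/35 or with equal SDs. These figures also assume normal data, a 5% Levene threshold, and that the test chooses between the pooled and Welch forms.

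The documents do not support the stronger reading that the primary comparison is materially mis-sized. They supply neither the imbalance nor the variances this would need, and even the 25/45 stress case stays between 4.2% and 6.1% two-sided. The gap that needs no assumption is that the threshold, the action and the sidedness of the analysis test are unstated.

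**What to change.** Replace the Levene sentence in Section V, Hypothesis 1.1-1.4, with: *The between-arm comparison uses the unequal-variance (Welch) t-test; no preliminary variance test is done.* State in the same place whether the test is one- or two-sided, and make it agree with the Power Analysis. If a regression or mixed model is adopted instead, use arm-specific residual variances or robust standard errors.

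The cost is one sentence, and the target of 35 per arm stays. On normal data the power loss is 0.1 point or less from 35/35 to 35/45 and at most 0.5 at 25/45. On skewed scores it may reach about 2 points at 25/45. Because one-sided Welch is not exactly 5% under skew, that limitation should be kept in mind if the one-sided form is chosen.

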[name] and [name] were investigators in a similarly designed multicenter trial involving meniscal tears in the knee.⁴³ In that recently published study, once enrolled, the patient retention rate was approximately 90%. We believe we will have similar success over the course of this study. Nevertheless, procedures will be in place to aid in maintaining subject participation over the course of the study. Outcome measures collected around formal visits can be collected remotely. Subjects can receive the surveys via email sent through REDcap. Study staff will conduct reminder phone calls around data collection time points.

IV. STUDY PROCEDURES:

Enrolled subjects will complete surveys around normal clinic visit intervals. Subjects will continue receiving surveys around their normal postoperative clinic visits until they request to stop receiving them. We are interested in long-term outcomes for these treatment arms, so we hope to collect patient-reported outcome measures for several years after randomization. These surveys can be completed remotely or at clinic visits. Follow up/reminder calls will be conducted to ensure subjects complete surveys.

Medical History:

The medical record may be reviewed for relevant medical history, imaging, physical exam, and surgical procedure from the subject's operative note, imaging, or clinic visit notes.

Patient-Reported Outcome Measures (PROMs) Surveys:

Pain/Physical Function:

Modified Harris Hip Score (mHHS): The MHHS is a validated condition specific outcome instrument that is used widely after hip arthroscopy. The eight questions measure domains of pain, gait function, and functional activities. Scores range from 0 (poor) to 100.1 (ideal).^{45,46}

The Lower Extremity Function Scale (LEFS): The LEFS is a 20 item validated outcome measure that is commonly used by physical therapists to initially evaluate and subsequently monitor patient progress through the course of a rehabilitation program. The minimum level of detectable change is 9 points.⁴⁷

Hip Outcome Score (HOS): The HOS is composed of the activities of daily living (HOS-ADL) subscale and the sports (HOS-sports) subscale. The HOS-ADL subscale contains 19 items pertaining to basic daily activities, and the HOS-sports subscale contains 9 items pertaining to higher-level activities, such as those required in athletics. In addition to the 5 potential responses, ranging from "unable to do" to "no

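### The effect-size formula divides the arm means where it should subtract them, so its grade does not measure the treatment effect

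*Combined protocol and SAP*

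**What the plan says.** In the combined protocol and SAP, Section V, under Hypothesis 1.1-1.4, mean mHHS at 12 months is compared between arms by independent t-test. The plan continues: "If a statistically significant difference is detected during these analyses, we will calculate the effect size (ES"), and gives the purpose as "to determine how meaningful these results are outside of being statistically significant". The formula is "mean mHHS score of surgical arm / mean mHHS of the conservative group) / standard deviation of the conservative group", with an inner bracket around the two means. The grading rule is "an ES <0.1 is trivial, ES of 0.1-0.3 is minimal, ES of 0.3-0.5, is moderate, and ES >0.5 is large".

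Elsewhere the plan measures the effect as a difference. The Power Analysis for Specific Aim 1 takes "a 10 point or greater difference on the mHHS as significant" and uses "a single-tail independent t-test to evaluate the difference between means with 80% power and a 5% significance level", with completers "in the appropriate proportion of 35 subjects per treatment arm". No other section restates or corrects the effect-size formula.

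**The concern.** A standardised effect size should be zero when the arms are equal, change sign when the direction reverses, and have no units. The printed quantity fails on all three counts. The ratio of two mHHS means usually lies near 1, so dividing it by the SD gives something close to 1/SD. Its grade then mainly reflects how variable the conservative arm is.

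The significance test does not depend on it. What is at stake is the interpretation of the primary result: applied literally, the rule could call a real benefit *trivial*, and it could not show a harm as a harm.

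**Working it through.** **Inputs from the documents.** Formula and cut-offs: Section V, Hypothesis 1.1-1.4. Planning difference of 10 points, 35 per arm, 80% power, one-sided 5% level: Section V, Power Analysis. Scale maximum of 100.1: Section IV, mHHS description.

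**Inputs not given.** The SD and the arm means are not stated. Both are assumed below and varied.

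**Step 1: the plan's own figure.** Without an SD, 35 per arm cannot be reproduced. It can only be solved for the SD it implies:

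- Normal approximation, one-sided: 10 / [(1.645 + 0.842) × √(2/35)] = 10 / 0.594 = 16.8.
- t-test power, one-sided: standardised difference 0.600, so SD = 10 / 0.600 = 16.66.
- t-test power, two-sided: standardised difference 0.679, so SD = 10 / 0.679 = 14.72.

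At these SDs the difference-form values of 0.60 and 0.68 restate the planning effect and are not independent evidence.

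**Step 2: properties that hold for any SD.** Let S and C be the surgical and conservative means.

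- S = C: as written, 1/SD. Difference form, 0.
- S < C: as written, still positive. Difference form, negative.
- Units: as written, 1/points. Difference form, none.
- Sensitivity: moving from 75 v 75 to 85 v 75 multiplies the written value by 85/75 = 1.13. Halving the SD doubles it.

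**Step 3: size, for assumed means of 85 v 75.** As written, (85/75)/SD = 1.1333/SD. Difference form, 10/SD.

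| SD | As written | Grade | Difference form | Grade |
|---|---|---|---|---|
| 8 | 0.142 | minimal | 1.25 | large |
| 10 | 0.113 | minimal | 1.00 | large |
| 12 | 0.094 | trivial | 0.83 | large |
| 14.72 | 0.077 | trivial | 0.68 | large |
| 16.66 | 0.068 | trivial | 0.60 | large |
| 20 | 0.057 | trivial | 0.50 | moderate (at the boundary) |

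The written value falls below 0.1 once the SD exceeds 1.1333/0.1 = 11.3.

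**Step 4: other cases.**

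- No effect, 80 v 80: as written, 0.125 at SD 8, 0.100 at SD 10 and 0.060 at SD 16.66. The correct value is 0. At SD 10 or below, no effect already reaches *minimal*.
- Surgery worse, 75 v 85, SD 16.66: 0.8824/16.66 = +0.053, against −10/16.66 = −0.60.
- Large benefit, 80 v 60, SD 12: 1.333/12 = 0.111. The written grade can therefore leave *trivial*.
- To reach *large* as written, S/C must exceed 0.5 × SD. Even with S at 100.1, C must be below 100.1/(0.5 × SD): 20.0 at SD 10, 13.6 at SD 14.72 and 12.0 at SD 16.66.

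**Step 5: what significance already implies.** With 35 per arm (68 df) and equal SDs, the smallest significant standardised difference is t × √(2/35):

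- One-sided: 1.668 × 0.2390 = 0.399.
- Two-sided: 1.995 × 0.2390 = 0.477 in absolute value.

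A significant result favouring surgery is therefore at least *moderate* on the plan's scale when the difference form is used, whatever the common SD. At SD 16.66 the one-sided minimum is 0.399 × 16.66 = 6.64 points. With C = 75, the written formula gives (81.64/75)/16.66 = 0.065, *trivial*. At that SD it stays *trivial* unless S exceeds about 1.67 times C (0.1 × 16.66).

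**The case against.** The strongest reply is that this is a typing slip. The inner bracket makes sense around a subtraction, the rest of the plan works with differences, and the same paragraph has another apparent slip: it describes a 12-month analysis and then says it will be repeated at 12 months. A minus sign misread when the PDF was converted cannot be excluded, although the second division uses the same slash. An analyst would probably compute a standardised difference anyway. All of this is plausible, but it explains the error without removing it. Followed literally, the rule misgrades. Corrected silently, the reported analysis departs from the written plan.

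The consequence is also narrow. The statistic is descriptive, decides no hypothesis and is calculated only after a significant test, and readers can still set the arm means against the 10-point threshold. That stands and limits the severity.

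Some examples may never arise. If the significance condition means the between-arm test, equal arms are never graded. If it also covers the paired tests against baseline, which the wording allows, they could be. Surgery being worse would be significant only under a two-sided test. The power section is one-sided, and the analysis section does not state the sidedness. These cases are best read as showing the missing zero and sign. The misgrading of a significant benefit does not depend on them.

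Finally, a number can of course be computed and placed on the scale. The criticism is that the resulting grade has no valid meaning.

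**Conclusion.** The concern holds. As printed, the formula is not a standardised effect size, and the cut-offs have no valid meaning for it. That conclusion needs no assumed figure.

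The size does rest on assumptions. Taking the SD back-solved from the power statement (16.7 one-sided, 14.7 two-sided) and assumed means of 85 v 75, the rule turns a *large* effect (0.60 or 0.68) into a *trivial* one (0.068 or 0.077). The statement that any significant benefit is at least *moderate* assumes 35 per arm and equal SDs. The hypothesis tests, sample size and 10-point planning difference are untouched. It should be corrected because it governs how a significant primary result is described, but it does not threaten the trial's main inference.

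**What to change.** Replace the formula with (surgical mean − conservative mean) / SD of the conservative group. Add that the cut-offs apply to the absolute value and that the sign is reported to show direction. Otherwise a negative value such as −0.60 would fall literally below 0.1 and be graded *trivial*.

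The cost is one line in Section V, with no new data and no change to the tests or the sample size.

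A separate reporting improvement, not part of this error, is to give the mean difference with its 95% confidence interval against the 10-point threshold, whether or not the test is significant.
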